7.1 Required Clinical Care Evaluations

	Screening	
	within 28 days of enrollment	within 14 days of enrollment
Written Consent	X	
Medical history	X	
Confirmation of hepatic metastases meeting study eligibility requirements	X	
Provider assessment for eligibility	X	
ECOG performance status	X	
Complete Blood Count with diff (CBC), INR		X
Total bilirubin		X
Pregnancy test (urine or serum) WOCBP		X ¹

¹For women of childbearing potential (WOCBP): urine pregnancy test within 14 days prior to study registration. If a urine test is positive or cannot be confirmed as negative, a serum pregnancy test will be required.

Medical History: This will be obtained during the standard of care pre-RE clinical visit with the treating interventional radiology. The Interventional radiologist will collect the information directly from the patient. At this time ECOG status will also be determined by the interventional radiologist

Laboratory values: The laboratory values (CBC, INR, total bilirubin, and Pregnancy test) will be gathered from Epic, as this testing is standard of care prior to RE.

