7.2 Research Related Sample Collection

	Prior to RE	Time post RE			
		1 week (± 6 days)	2 weeks (±7 days) optional	4 weeks (± 2 weeks)	12 weeks (± 2 weeks)
Assess for adverse events		X	X	X	X
Peripheral blood for cytokines	X	X		X	X
Peripheral blood for lymphocytes	X	X		X	X
Tumor biopsy	X		X a treated and an untreated tumor		

Research sample collection will be tied to the clinical care time points whenever possible. It is recognized that with novel therapies as used in this study, the timing of protocol directed research samples may miss important patient specific events. For this reason, up to 3 extra samples for a total of 180 ml of blood may be drawn at additional time points that are not specified above. This blood would be drawn in the case that blood draws from specified time points were damaged, lost, or unusable.

7.3 Endpoints, detailed:

The primary endpoint for this study is to determine changes in the peripheral blood monocytes after RE therapy for primary and secondary malignancies of the liver at 12 weeks.

Secondary endpoints include the changes in peripheral blood monocytes at 7 days and 4 weeks. The changes in immunologically relevant cytokines (*IL-1 α , IL-1 β , IL-2, IL-6, IL-10, IL-12p70, IL-18, TNF α , IFN- γ , Fit ligand 3, and MCP-1*) at 7 days, 4 weeks, and 12 weeks will also be determined. Biopsies of the treated tumor prior to treatment and 2 weeks after treatment (if done) will also be performed to assess immune cell infiltration following treatment. The 2-week after treatment biopsy will be performed strictly for research purposes and will be optional. The second biopsy was made optional as it was found to be a significant barrier to enrollment. Furthermore, the change in PBMCs is the most scientifically important aspect of the study. Additionally, when available, a non-treated tumor will be biopsied two weeks after treatment to assess for immune cell infiltration.

7.4 Research data collection and lab analyses detailed:

Basic characteristics of the malignancy (type of malignancy, size of largest tumor, and number of tumors) will be recorded. RE will be completed in a manner which has been previously described (20). All of the preprocedural work up and procedure costs will be billed to insurance as this is standard of care.

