Clinical follow up with magnetic resonance imaging (MRI) or CT will occur at 1 month and 3 months. Radiologic response will be evaluated at 3 months using Response Evaluation Criteria in Solid Tumors (RECIST) and modified RECIST guidelines. Overall survival will be defined as time from RE to death, and patients will be censored for transplantation. Progression free survival will be defined as time from RE to progression as defined by RECIST and mRECIST.

Peripheral blood monocytes will be collected and processed for flow cytometric analyses and cryostorage for later batch studies. The effect RE on lymphocyte repertoire, numbers and phenotype will be assessed at baseline and at defined time points during the trial (7 days (+/- 6 days), 4 weeks (+/- 2 weeks), and 12 weeks (+/- 2 weeks). The frequency and percentage of peripheral blood monocytes and T-cell subsets (CD4 and CD8 effector memory, central memory and Treg subsets), NK cells and myeloid-derived suppressor cells will be determined. Peripheral blood tumor-specific T cell subsets will be evaluated by flow cytometry in cooperation with the Translational Therapy Laboratory, Masonic Cancer Center. Cytotoxic T lymphocytes (CD8+ T cells) and CD4+ helper T cells will be isolated using fluorescence-activated cell sorting (FACS) from cryopreserved cells followed by mRNA expression analysis to assess gene expression changes resulting from therapy. Testing will be performed in the UMN Flow Cytometry and Genomics Core Laboratories. Peripheral blood monocytes may also be tested in functional assays (i.e. IFN- γ ELISpot) for responses to known antigens as well as to predicted neoantigens from whole-exome/transcriptome sequencing of melanoma tumors. All patients will also undergo HLA testing to enable epitope discovery using available MHC binding prediction algorithms.

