On the day of RE patients will have labs drawn, as is consistent with current practice. In addition to standard labs (total bilirubin, international normalized ratio (INR), complete blood count (CBC)) the patients will have an additional tube drawn to be analyzed for cytokine level. To determine the effects on cytokines (*IL-1 α , IL-1 β , IL-2, IL-6, IL-10, IL-12p70, IL-18, TNF α , IFN- γ , Fit ligand 3, and MCP-1*) over a period of time the cytokines will be analyzed following RE at 7 days (+/- 6 days), 4 weeks (+/- 2 weeks) and 12 weeks (+/- 2 weeks). All cytokines will be measured in a similar way through the Cytokine Reference Laboratory at the UMN. This Clinical Laboratory Improvement Amendments (CLIA) approved lab specializes in the analysis of cytokines, chemokines, and growth factors, and as such is very qualified to perform these tests which they have been performing for several years on a regular basis. The tests will be performed in a similar fashion to prior authors (15-17).

The blood cells, blood serum and the biopsy samples will then be stored at the clinical research lab at the University of Minnesota

8 Event Monitoring, Documentation, and Reporting

Toxicity and adverse events will be classified and graded according to NCI's Common Terminology Criteria for Adverse Events version 5.0 (CTCAE V5) and reported on the schedule below. A copy of the CTCAE can be downloaded from the CTEP home page. (http://ctep.cancer.gov/protocolDevelopment/electronic_applications/ctc.htm#ctc_50).

The following definitions of adverse events (AEs) and serious adverse events (SAEs) will determine whether the event requires expedited reporting via the SAE Report Form in addition to routine documentation in the OnCore AE case report form (CRF).

Note: throughout this section the generic term "study drug" refers to the study related procedures.

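### Section 7.4 promises lymphocyte numbers after RE, but the plan gives no way to obtain them: no post-RE blood count is scheduled or collected and no absolute-count flow method is named

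*Combined protocol and SAP*

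**What the plan says.** Section 7.4 lists lymphocyte numbers among the outcomes: "lymphocyte repertoire, numbers and phenotype will be assessed at baseline and at defined time points during the trial". The follow-up times are 7 days, 4 weeks and 12 weeks. The cells are "processed for flow cytometric analyses and cryostorage for later batch studies", and the readout begins "The frequency and percentage of peripheral blood monocytes and T-cell subsets", continuing with NK cells and myeloid-derived suppressor cells. No unit per volume of blood, parent population or counting method is given.

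Blood counts appear in two places, both before RE. The screening table in 7.1 has "Complete Blood Count with diff (CBC), INR" within 14 days of enrollment, and the values are taken from the medical record "as this testing is standard of care prior to RE". The 7.4 text on cytokines places a CBC among the standard labs on the day of RE and does not mention a differential.

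After RE, the 7.2 table has a row "Peripheral blood for lymphocytes" at 1, 4 and 12 weeks, a cytokine row at the same times, adverse event assessment and the optional biopsy. It has no CBC row. The clinical follow-up in 7.4 names imaging only: "Clinical follow up with magnetic resonance imaging (MRI) or CT will occur at 1 month and 3 months".

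Section 10 fits a mixed model to a peripheral lymphocyte value, separately for each lymphocyte type, and does not say whether that value is a count or a percentage.

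**The concern.** The primary objective is the change in peripheral blood lymphocytes, and 7.3 calls the change in PBMCs the most important scientific aspect of the study. Unless a counting method is built in, flow cytometry on processed cells gives each subset as a share of some parent population. Turning a share into cells per microlitre needs a total from the same draw, and the plan provides none after RE.

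Shares of one parent sum to 100%, so a fall in one component raises the others. Because Section 10 models each subset separately, a relative rise could be reported as an expansion of, say, effector or regulatory cells when the number of those cells in blood had fallen. An overall lymphocyte loss that left the mix unchanged would not show at all. Either error would affect the main blood outcome, and a total not taken at the visit generally cannot be recovered later from stored cells unless blood volume and cell yield were recorded.

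**Working it through.** The documents state no expected count, percentage, effect size or SD for this outcome, so there is no figure of theirs to reproduce. The check has two parts.

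**1. Is there a total at each lymphocyte draw?**

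| Draw | Blood count in the plan | Differential stated? |
|---|---|---|
| Screening (7.1) | CBC, within 14 days of enrollment | Yes |
| Day of RE (7.4) | CBC among standard labs | No |
| 1 week (7.2) | None | – |
| 4 weeks (7.2, 7.4) | None | – |
| 12 weeks (7.2, 7.4) | None | – |

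No bead, volumetric or yield-per-volume method is described for any draw. The baseline is also weak: the count with a differential is the screening one, which need not fall on the day of the baseline flow sample.

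**2. What can a share hide?**

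Subset count = total lymphocytes × subset share. If the share rises by a relative amount r and the total falls by a fraction f, then

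change in count = (1 + r)(1 − f) − 1.

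The count falls while the share rises when f > r/(1 + r):

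| Relative rise in share, r | Break-even fall in total, r/(1 + r) |
|---|---|
| 10% | 0.10/1.10 = 9.1% |
| 20% | 0.20/1.20 = 16.7% |
| 30% | 0.30/1.30 = 23.1% |
| 50% | 0.50/1.50 = 33.3% |
| 100% | 1.00/2.00 = 50% |

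Illustration with assumed values, none from the documents: baseline total 1.5 ×10⁹/L and subset share 25%, so the count is 1.5 × 0.25 = 0.375. After RE the share reads 30%, a relative rise of 20%.

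| Fall in total | Subset count after RE | Change in count | Change in share |
|---|---|---|---|
| 0% | 1.50 × 0.30 = 0.450 | +20% | +20% |
| 10% | 1.35 × 0.30 = 0.405 | +8% | +20% |
| 20% | 1.20 × 0.30 = 0.360 | −4% | +20% |
| 30% | 1.05 × 0.30 = 0.315 | −16% | +20% |
| 50% | 0.75 × 0.30 = 0.225 | −40% | +20% |
| 70% | 0.45 × 0.30 = 0.135 | −64% | +20% |

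The share reads +20% in every row; only a total at the same draw tells the rows apart.

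The reversal needs an uneven loss. In the 30% row the subset falls from 0.375 to 0.315 (−16%), while all other lymphocytes fall from 1.125 to 1.05 − 0.315 = 0.735 (−35%). If every subset instead falls by the same 30%, the subset count is 0.375 × 0.70 = 0.2625 and the share is 0.2625/1.05 = 25%, unchanged. That loss is missed, not reversed.

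**The case against.** The strongest reply is that an unnamed method is not an absent one. Section 7.4 names two readouts, frequency and percentage, and the first may mean a count; flow cytometry can give absolute counts with beads or volumetrically. The tables are also weak evidence of absence. The 7.1 table covers screening only and 7.2 covers research collection, while the day-of-RE CBC and the follow-up imaging appear only in text. Section 7.2 ties research draws to clinical visits where possible, and screening values already come from the medical record, so routine post-RE counts may exist.

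This stands as far as it goes. A reader might infer that numbers cannot be obtained after RE; the documents do not support that, only that the plan gives no way to obtain them. The gap remains, because no counting method is described and no routine post-RE count is scheduled or collected. With windows of ±6 days and ±2 weeks, a same-day match is not assured.

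Three further limits hold:

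- Absolute lymphocyte count × share does not fit monocytes or myeloid-derived suppressor cells, and memory subsets reported within CD4 or CD8 need their parent fractions too.
- Percentages are a legitimate measure of composition, and 7.4 also lists repertoire and phenotype.
- 7.3 calls the primary variable monocytes, while 1.1 and Section 10 say lymphocytes. That is a separate matter to reconcile, but it adds to the need to name the variable and its unit.

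**Conclusion.** The point holds and should be corrected. Followed as written, the plan could yield only shares for its main blood outcome at all three post-RE times, although it promises numbers. The size is conditional: a share up by a relative 20% hides a falling count once the total falls by more than 16.7%, and a share up by 50% once it falls by more than 33.3%. These thresholds are arithmetic identities and rest on no trial data. The 1.5 ×10⁹/L and 25% in the illustration are assumptions.

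Three stronger readings should be resisted. One is that the sign will in fact be reversed: no expected fall in lymphocytes is given, so the frequency is unknown. Another is that any general loss would appear as an increase: an even loss leaves shares unchanged and would be missed. The third is that numbers are secure before RE and lacking only afterwards: the day-of-RE CBC mentions no differential, so the baseline needs the same repair. The point changes no sample size, significance level or patient care; it bears on what the primary result can be said to show.

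**What to change.** **Section 7.2.** Secure a total at every lymphocyte draw (day of RE, 1, 4 and 12 weeks) in one of three ways: a CBC with differential from the same venepuncture; abstraction of a same-day routine CBC with differential where one exists; or a single-platform absolute-count flow method, named in 7.4.

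**Section 10.** State the unit. Analyse each subset as cells/uL beside its percentage of a named parent population, and say in advance which of the two carries the primary analysis. Use the matching parent count:

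- T and NK subsets: the absolute lymphocyte count.
- Memory and Treg subsets: the lymphocyte count carried through each parent gate.
- Monocytes and myeloid-derived suppressor cells: the monocyte or total mononuclear cell count.

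Describe changes in percentage as changes in composition, and claim expansion or loss of cells only from the counts.

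**Cost.** One small extra tube where blood is already drawn, or chart abstraction, with a minor laboratory charge. Visits already past without a matching count will have percentages only, and the report should say how many those are.

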- Determine changes in the peripheral blood cytokines after radioembolization (RE) therapy for primary and secondary malignancies of the liver.
- Determine the changes in infiltrating immune cells within the treated tumor, which occur after RE therapy for primary and secondary malignancies of the liver.

- Determine the changes in infiltrating immune cells within non-treated liver tumors, which occur after RE therapy for primary and secondary malignancies of the liver.
- Determine changes in the peripheral blood lymphocytes after RE therapy for primary and secondary malignancies of the liver at 7 days, 4 weeks, and 12 weeks.

Key Inclusion Criteria:

- Biopsy or image (in the setting of hepatocellular carcinoma (HCC)) diagnosed hepatic malignancy
- Total bilirubin < 2 mg/dL
- ECOG status ≤ 2
- Life expectancy >3 months assessed
- Age >22 years
- Lesion >2.0 cm which is amenable to percutaneously biopsied

Key Exclusion Criteria:

- Unwilling or unable to attend all study related follow ups
- Technetium 99 macro aggregated albumin (MAA) lung shunt fraction >20%
- Arterial anatomy which precludes the ability to safely perform RE
- INR > 3 or platelet count <15,000 which cannot be corrected
- Patients who are unable to hold anticoagulation and/or antiplatelet therapy in the peri-procedural setting

Accrual Objective:

The goal is to accrue 30 patients. It is anticipated that approximately 10 patients per year can be enrolled; meaning enrollment is expected to take 60 months.

1 Objectives

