Patients will undergo biopsy of the largest percutaneous available tumor to be treated within a 12-week period prior to treatment and optionally at 2 weeks (\pm 7 days) following RE. If the pre-treatment biopsy is not standard of care, it will be done for research. The 2-week after treatment biopsy will be performed strictly for research purposes. The optional post RE biopsy will include a treated (defined as a lesion which had y90 delivered to it as determined on standard of care Bremsstrahlung scan after RE) and non-treated lesion (defined as a lesion which did not receive y90 as determined on standard of care Bremsstrahlung scan after RE). Four 18-gauge core needle biopsies will then be obtained. One of the four cores will immediately be placed on ice and sent to our CLIA approved research laboratory. This sample will then be flash frozen and

stored at -80 degrees. Three of the cores will immediately be placed into formalin and submitted to the research laboratory where they will undergo paraffin embedding. These samples will also be stored until analysis can be undertaken. A paraffin embedded sample will then undergo immunohistochemistry analysis. The samples will be analyzed using a standard streptavidin biotinylated alkaline phosphatase method or a streptavidin biotinylated horseradish peroxidase method as described previously (17,18). The slides will then be analyzed using a standard light microscope and CCD-camera at 20x objective. The slides will be scanned into digital format using an Aperio XT scanner (Leica Biosystems Inc. Buffalo Grove, IL). A pathologist will then demarcate the tumor area on the slide. This area of interest will be analyzed using the counting software "FiJI-ImageJ" (FIJI) will be used to quantify the number of infiltrating cells (cell/mm²) in the tumor. They will also be analyzed by the number of infiltrating cells per 100 tumor cells. These analytic standards have been previously described (17,18). The infiltration of immune cells into the tumor before and after treatment will then be compared with each patient serving as their own control.

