9.4 Record Retention

The investigator will retain study records including source data, copies of case report form, consent forms, HIPAA authorizations, and all study correspondence in a secured facility for at least 6 years after the study file is closed with the IRB.

10 Statistical Considerations

Descriptive statistics will be calculated for outcomes and variables of interest. Continuous variables will be summarized using mean and standard deviation, or median and interquartile range, as appropriate. Categorical variables will be summarized using frequencies and percentages. Plots of each peripheral lymphocyte at baseline and each subsequent time of measurement (as stated in the protocol synopsis section) will be generated. This will help determine if individuals have different baseline peripheral lymphocyte values or different peripheral lymphocyte value trends over time. Similar plots will be generated for each cytokine (*IL-1 α* , *IL-1 β* , *IL-2*, *IL-6*, *IL-10*, *IL-12p70*, *IL-18*, *TNF α* , *IFN-Y*, *Fit ligand 3*, and *MCP-1*).

Primary analysis: To determine if there is a change in peripheral lymphocytes following RE, a mixed model with random intercept and random slope for time, and adjustment for baseline peripheral lymphocyte value will be carried out for each lymphocyte. The fixed effect for time, representing the slope over time, will be tested for significance, and a 95% confidence interval will be reported. Depending on if the outcome is skewed, appropriate transformations will be used. Similar models may be carried out with adjustment for certain variables such as age, sex, and size of tumor. Additionally, to investigate specific changes in peripheral lymphocytes from baseline, pairwise comparisons between baseline and each measurement following RE, using paired t-tests or Wilcoxon signed-rank tests, will be performed with a Bonferroni adjustment for multiple comparisons.

Secondary analysis: To determine if there is a change in active cell infiltration into tumors following RE, paired t-tests or nonparametric Wilcoxon signed-rank tests will be used, depending on the distribution of the outcome. These analyses will be performed for the different tumor types (treated and non-treated tumors). In the case that certain variables such as age, sex and size of tumor are of interest, a mixed model will be obtained using an appropriate distribution assumption of the outcome (e.g. Gaussian, Poisson or negative binomial).

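### The pre-RE tumour biopsy may be up to 12 weeks old, but the paired infiltration analysis takes no account of its age or of therapy given before RE

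*Combined protocol and SAP*

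**What the plan says.** The synopsis lists as a secondary objective: "Determine the changes in infiltrating immune cells within the treated tumor, which occur after RE therapy". Section 7.4 gives the only explicit window for the baseline sample: "Patients will undergo biopsy of the largest percutaneous available tumor to be treated within a 12-week period prior to treatment". It adds: "If the pre-treatment biopsy is not standard of care, it will be done for research". A standard-of-care biopsy inside the window therefore counts as the baseline. The table in Section 7.2 puts the post-RE biopsy at "2 weeks (±7 days) optional". For the baseline, the synopsis and that table say only that it comes before treatment.

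Section 7.4 then states the comparison: "The infiltration of immune cells into the tumor before and after treatment will then be compared with each patient serving as their own control". Section 10 supplies the test: "paired t-tests or nonparametric Wilcoxon signed-rank tests will be used, depending on the distribution of the outcome". A model with covariates is conditional: "In the case that certain variables such as age, sex and size of tumor are of interest, a mixed model will be obtained". Biopsy age and therapy before RE are not among the examples.

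The tumour characteristics to be recorded under Section 7.4 are type, size of the largest lesion and number of lesions. Sections 3.1 and 3.2 place no limit on anticancer therapy between the baseline biopsy and RE. The blood baseline, by contrast, is drawn on the day of RE (synopsis and Section 7.4).

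**The concern.** A design in which each patient is his or her own control attributes the full before/after difference to whatever happened between the two samples. To read that difference as the effect of RE, the first sample must describe the tumour shortly before RE. If it is weeks old, the difference also contains natural change in the tumour and the effect of any treatment given in the gap. No concurrent group is available to subtract these.

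The plan also pools patients whose baselines have very different ages. The interval between biopsies can run from about 1 week (baseline just before RE, second biopsy at day 7) to 15 weeks (12 + 3). This spread adds variability to an endpoint that can be measured only in patients who accept an optional second biopsy. At stake is what the trial may say about infiltration after RE, which it presents as a secondary objective.

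**Working it through.** The plan gives no effect size, standard deviation or sample-size calculation for infiltration, so there is no stated figure to reproduce. The check is of timing.

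**Inputs.** Let b be the days from baseline biopsy to RE, 0 to 84 (12 × 7; Section 7.4). Let p be the days from RE to second biopsy: 7, 14 or 21 (14 ± 7; Section 7.2).

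**Formula.** Share of the between-biopsy interval that precedes RE = b / (b + p).

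| Baseline age b | p = 7 | p = 14 | p = 21 |
|---|---|---|---|
| 84 days | 84/91 = 92.3% | 84/98 = 85.7% | 84/105 = 80.0% |
| 42 days | 85.7% | 75.0% | 66.7% |
| 28 days | 80.0% | 66.7% | 57.1% |
| 14 days | 66.7% | 50.0% | 40.0% |
| 7 days | 50.0% | 33.3% | 25.0% |

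The share exceeds one half whenever b > p. Any baseline older than 21 days therefore puts most of the interval before RE, wherever the second biopsy falls in its window.

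**How common this would be.** The documents give no distribution of biopsy ages. If ages were uniform over 0 to 84 days (an assumption), the fraction of pairs with b > p would be 1 − 14/84 = 83%, ranging from 1 − 21/84 = 75% to 1 − 7/84 = 92%.

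**What it could do to the test.** This part is illustration only. Assume no RE effect, a second biopsy at 2 weeks, and linear drift of d standard deviations of the paired difference per week, over the whole interval. The noncentrality of the paired t-test is d × (baseline age in weeks + 2) × √n. For n = 20 pairs, d = 0.02 and a 12-week-old baseline in every patient, it is 0.02 × 14 × √20 = 1.25. Rejection rates at two-sided 0.05 are:

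| Pairs | Drift per week | 12 weeks old | 4 weeks old | 1 week old |
|---|---|---|---|---|
| 10 | 0.02 SD | 12.5% | 6.3% | 5.3% |
| 10 | 0.05 SD | 50.6% | 13.6% | 7.1% |
| 20 | 0.02 SD | 22.1% | 8.0% | 5.7% |
| 20 | 0.05 SD | 84.4% | 24.7% | 9.8% |

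The drift rates, the number of pairs and the common baseline age are all assumed. The table shows how strongly the test depends on quantities that the plan neither controls nor records. It does not estimate the error rate of this trial.

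**The case against.** **Time is not bias.** A reader might infer that 80% to 92% of any observed change will be unrelated to RE. The documents do not support that. If infiltration is stable and no therapy intervenes, an old baseline does no harm on average. Added variability alone costs precision and does not invalidate a paired test. This stands, and it limits the size of the claim.

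**Research biopsies may already be bounded.** Section 3.1.7 requires consent before research procedures, Section 7.1 puts consent "within 28 days of enrollment", and Section 4.2 completes enrollment by entering an on-treatment date. If that date is the day of RE, a biopsy done only for research already falls within about 28 days of it. The date is not defined, and Section 7.4 states 12 weeks without this qualification. The argument narrows the problem toward standard-of-care tissue but does not remove it.

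**Old diagnostic tissue may not qualify.** Section 7.4 describes four cores with immediate research handling. If that applies at both time points, stored tissue would often be unsuitable. The wording leaves open whether it covers the baseline.

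**A breach of the screening window.** A reader might infer that the biopsy conflicts with the 28-day limit in Section 7.1. It does not: that window runs to enrollment rather than to RE, and the table lists no research biopsy.

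**Untreated lesions as context.** They help little. Section 7.3 has them biopsied only when available, the Section 7.2 table names them only after RE, and change in them is itself a secondary objective.

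**A hard cut-off has a price.** Limiting the main analysis to baselines within 28 days could discard many pairs from a small subset, and 57% to 80% of the interval at that limit would still precede RE. This stands, and is a reason not to restrict the main analysis.

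**Conclusion.** The point holds as a weakness in the secondary infiltration endpoints. The plan permits a baseline up to 84 days old and does not adjust for its age. It provides for no record of intervening therapy and no sensitivity analysis. At the limit, 80% to 92% of the between-biopsy time precedes RE, and for any baseline older than 21 days the larger part does. The direction and size of any bias are unknown, because drift, intervening therapy and the distribution of biopsy ages are not given.

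The lymphocyte and cytokine analyses are not affected, since their baseline is drawn on the day of RE. Section 7.3 ranks the change in blood mononuclear cells as scientifically most important. A reader should therefore not extend this point to the primary result. It is worth correcting because biopsy pairs will be scarce (at most 30, with the second biopsy optional) and the correction is cheap.

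**What to change.** **Section 7.4.** Schedule a pre-RE biopsy done solely for research as close to RE as practicable, for example within 28 days. That figure is a pragmatic limit and is not derived from the screening window; it cuts the longest pre-RE gap from 84 to 28 days. State that no biopsy is repeated if RE is delayed. For every patient, record the biopsy date and any anticancer therapy between biopsy and RE.

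**Section 10.** Keep all pairs in the main infiltration analysis. Pre-specify a sensitivity analysis limited to pairs with a recent baseline and no intervening therapy, using for example 28 days or less and also 14 days or less. Add a display of each patient's change against the biopsy-to-RE interval. Attribute change to RE only if the recent-baseline result agrees with the main one in direction and size, judged on estimates and confidence intervals rather than on whether each reaches significance.

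**Cost.** Protocol wording, two data items, one sensitivity analysis and one plot, with no planned extra biopsy. The restricted analysis will have few pairs and low precision. How few cannot be said from the documents, so it may be inconclusive; the report should then describe the infiltration change without attributing it to RE.

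### The protocol does not provide for masking of the pathologist who outlines the tumour area, and that outline decides which tissue is counted in the before/after infiltration comparison

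*Combined protocol and SAP*

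**What the plan says.** The reading procedure is in Section 7.4 (research data collection and lab analyses).

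- After staining and scanning, "A pathologist will then demarcate the tumor area on the slide".
- The outline is the input to the software: "This area of interest will be analyzed using the counting software".
- There are two readouts. The first is to "quantify the number of infiltrating cells (cell/mm²) in the tumor". For the second, "They will also be analyzed by the number of infiltrating cells per 100 tumor cells".
- The standards for this analysis are referred to references 17 and 18.
- The comparison is paired: "The infiltration of immune cells into the tumor before and after treatment will then be compared with each patient serving as their own control".

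Section 10 gives the test: "paired t-tests or nonparametric Wilcoxon signed-rank tests will be used", applied to treated and to non-treated tumours. Infiltration in each kind of lesion is a secondary objective (Synopsis and Section 1.2). Section 7.3 makes the 2-week biopsy optional.

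**The concern.** Counting by software makes the count reproducible once the area is fixed, but it cannot correct the choice of area. That choice is a human judgement, and the comparison it feeds is before against after RE. Time point is therefore the one fact the person drawing the outline should not know.

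The plan also gives that person an expectation. Section 2 describes an earlier study that found more immune cells in treated tumours after RE, and it argues that RE may be well suited to producing systemic immune effects. There is no control group, so a habit of outlining post-RE slides differently would not cancel. It would appear as a change in infiltration.

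**Working it through.** **Step 1: is masking provided for?** Section 7.4 describes core handling, staining, scanning, outlining and counting. It does not mention masking, coded labels, reading order, number of readers or a rule for drawing the outline. Sections 7.2, 7.3 and 10 add none of these. Nor does any section say that the pathologist knows the time point. The documents are silent, and references 17 and 18 cannot be consulted here.

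**Step 2: how can the outline change the result?** The plan states no figure to reproduce, so this is an illustration on assumed inputs. Let f be the share of the outlined area that is not tumour, and r the density of counted cells in that tissue relative to tumour. Then

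measured density / true tumour density = 1 + f(r − 1).

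If the outline contains such tissue at one time point and not at the other, the spurious change is f(r − 1):

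| f | r = 0.5 | r = 1 | r = 2 |
|---|---|---|---|
| 5% | −2.5% | 0% | +5% |
| 10% | −5% | 0% | +10% |
| 20% | −10% | 0% | +20% |

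The middle column matters. A larger or smaller outline over tissue of uniform density loses or gains cells and area in proportion, and cells/mm² does not move. Bias needs the outline to shift toward denser or sparser tissue, and to do so differently by time point.

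The per-100-tumour-cells readout does not have area as its denominator, so this formula does not apply to it directly. It can still be affected if the outline selects the region in which both cell types are counted.

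**Step 3: what would a systematic shift do to the test?** Assume no true change and a reader-induced shift of b standard deviations of the paired difference. For n pairs, the two-sided 5% paired t-test rejects with probability P(|T| > t₀.₉₇₅,ₙ₋₁), where T is noncentral t with n − 1 degrees of freedom and noncentrality b√n. For n = 20 and b = 0.2 the noncentrality is 0.2 × √20 = 0.89.

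| Pairs | b = 0 | b = 0.1 | b = 0.2 | b = 0.3 |
|---|---|---|---|---|
| 10 | 5% | 5.9% | 8.8% | 13.6% |
| 20 | 5% | 7.1% | 13.6% | 24.7% |
| 30 | 5% | 8.3% | 18.5% | 35.5% |

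Thirty is the accrual goal and so the ceiling on pairs; the optional biopsy makes the actual number unknown. The documents give no standard deviation, effect size or reader-variability figure for infiltration, so no value of b can be preferred. More pairs do not help: a fixed bias becomes easier to declare significant.

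**The case against.** The strongest reply is that silence is not evidence of unmasked reading. A reader might infer that the pathologist will know which slide is which. The documents do not support that. Coding may sit in a laboratory procedure, or in the cited standards. This stands, and the point is limited to what the protocol leaves unspecified. It does not remove the need, because a safeguard for a before/after comparison should be visible in the plan, and one sentence would suffice if it already exists.

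A reader might also infer that a tighter outline automatically inflates density: 10% smaller gives 1/0.9 = 1.11, or +11%, and 20% smaller gives 1/0.8 = 1.25, or +25%. Those figures hold only if the excluded tissue contains no counted cells. If it has the same density the change is 0%; if it is denser the sign reverses.

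A third inference would be that a treated-versus-untreated contrast is at risk. Section 10 specifies paired before/after tests for each kind of lesion and no direct test between them. Masking to time point is therefore the main need, and masking to lesion status comes second.

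Finally, the reach is limited. The endpoint is secondary, the second biopsy is optional, and Section 7.3 itself ranks the blood-cell changes as scientifically most important. All of that is correct and sets the weight of the point.

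**Conclusion.** The point holds as a low-cost improvement. A pathologist's judgement selects the tissue on which the paired infiltration comparison rests, and the documents make no provision for masking that judgement. If outlines drift toward denser or sparser tissue differently before and after RE, cells/mm² will be biased, and the per-100-tumour-cells measure possibly so.

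The size and direction of any real shift cannot be derived from the documents. The tables above rest on assumed values of f, r and b, and include cases with no bias at all. The consequence is confined to the secondary infiltration objectives in patients with the optional post-RE biopsy. The blood-based primary endpoint is not affected.

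**What to change.** In Section 7.4, state that:

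- scanned slides carry a random code that hides patient, time point and treated/non-treated status;
- the same pathologist outlines all areas in one batch, in random order;
- the code is released only after the counts are locked.

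This fits the existing sample flow, since "These samples will also be stored until analysis can be undertaken" and slides are digitised in any case. The cost is relabelling work by the laboratory. It needs no extra tissue, visits or patients, and no change to the tests or the significance level.

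Masking may remain incomplete, because some post-RE slides may be recognisable from treatment change or from microspheres. The protocol should say so and name it as a limitation. If references 17 and 18 or a laboratory procedure already require coded reading, a sentence stating that would meet the masking part of this point.
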